1.3 Benefit/risk and ethical assessment

Benefit:

Evidence showed that XZK treatment by reducing LDL-C levels and TG levels significantly reduces the risk of CHD events by 45%. Therefore, for the clinical benefit of dyslipidemia patients with prediabetes , they will get expert advice and guidance of lipid management from physicians.

Potential risk:

Risk associated with Study Drug:

XZK capsule is a modernized proprietary Chinese medicine product with modern pharmaceutical technology and strict Good management practices (GMP)production management. A few mild or moderate gastrointestinal (GI) effects may occur when taking XZK, but a large number of clinical application results show that XZK capsule is safe and with few side effects [1].

Atorvastatin decrease cholesterol production in the liver by preventing the conversion of HMG-CoA to mevalonate. Common side effects to Atorvastatin include gastrointestinal (GI) effects, headache, and mild muscle pain. Rare side effect include rhabdomyolysis, dark urine, jaundice, etc.

Participants with high potential risk (meet one of the Exclusion Criteria) will not be eligible for enrollment . Moreover, we will minimize this risk by mandating adequate follow-up visit to ensure clinical assessment(e.g.CK and liver enzymes (ALT, AST)) during study participation . Local Investigator and the sponsor will also collect and report serious adverse events according to regulations. The study drug will be discontinued immediately, if any ADR occurs during the study.

Risk associated with Study Procedure:

In view of the few patients with prediabetes receive drug treatment and Statins are the most effective and acceptable drugs to treat dyslipidemia, patients may be initially hesitant to participant in this study. Previous studies have reported that XZK is effective in blood lipid reduction. We will provide the patients with pre-study education on dyslipidemia medication therapy.

Loss to follow up is another risk factor which can affect the incident rate in statistical analysis and outcome. However, this study is designed for 24 weeks short intervention and contains 5 visits with the assistance of local investigators and experienced CRO team. Therefore, we are confident to limit the loss to follow up rate.

1.4 Study Design

1.4.1 Overall design

Xtreme study is a prospective, randomized, open-label, multi-center trial. The primary objective of the study is To determine whether XZK 1200mg/d, compared to atorvastatin 20mg/d, has a favorable impact on HbA1c levels from baseline to 24 weeks in dyslipidemia patients with prediabetes.

1.4.2. Randomization

Randomization of participants that meet all inclusion criteria and do not have any exclusion criteria will be randomly allocated in a 1:1 ratio to XZK group (xuezhikang [1200mg/d]) or ATV group (atorvastatin [20mg/d]) stratified by center and age(≥ 60 years old, < 60 years old) Randomization will be done using a central, automated, web-based electronic randomization software. Randomization will occur within 3 days after the Laboratory result of randomization visit reported .

1.4.3. Minimizing Sources of Bias

Because treatment will be open-label, blindly tested of outcomes will be conducted by adjudicators who are unaware of treatment allocation.

1.4.4 Number of Centers

This study will include approximately 20 sites in China.

1.4.5 Number of Participants

There will be approximately 392 subjects randomized in this study. Justification for the sample size can be found in 8.1 Sample size estimate.

1.4.6 Estimated Study Duration

Enrollment period will last from July 2022 to July 2023.

1.4.7 Study Duration for Participants

After signing the informed consent, subjects should be randomized within 7 days.

The follow-up duration of study participants will be 24 weeks after randomization.

1.4.8 End of Study

A subject is considered to have completed the study if he/she has completed all phases of the study including the last subject's last Follow-up or Early Discontinuation Visit.

2 STUDY OBJECTIVES

2.1 Primary Objective

The primary objective of Xtreme is:

To determine whether XZK 1200mg/d, compared to atorvastatin 20mg/d, has a favorable impact on HbA1c levels from baseline to 24 weeks in dyslipidemia patients with prediabetes

2.2 Secondary Objective

Secondary objectives include:

(1) To evaluate the impact of XZK 1200mg/d on fasting plasma glucose (FPG), post prandial glucose (PPG) 2h and insulin production index levels compared with atorvastatin 20mg/d after 24 weeks of treatment in dyslipidemia patients with prediabetes.

(2) To evaluate change in LDL-C levels and non HDL-C after 24 weeks of treatment with XZK 1200mg/d as assessed by percentage change from baseline.

2.3 Safety

According to the routine procedure, adverse events, abnormal physical examination and abnormal laboratory data (ALT, CK, etc.) will be observed after randomization

3 STUDY POPULATION

Multiple strategies will be used to identify potentially eligible participants for this study. Only subjects that meet all of the inclusion criteria and none of the exclusion criteria listed below will be randomized into the study.

The Investigators are expected to maintain a patient log (Appendix I) of all potential study candidates that include limited information about the potential candidate (eg, date of screening). Before any study-specific procedure, the appropriate written informed consent must be obtained.

3.1 Inclusion Criteria

Participants are eligible to be included in the study only if all of the following criteria apply:

1. Written informed consent provided
2. Age ≥ 40 years
- (5) Diagnosed Prediabetes, meeting one of the following conditions:
 - ✓ Impaired fasting glucose (IFG): $5.6 \text{ mmol/L} \leq \text{FPG} < 7.0 \text{ mmol/L}$;
 - ✓ Impaired glucose tolerance (IGT): $7.8 \text{ mmol/L} \leq 2\text{h PPG during } 75\text{g OGTT} < 11.0 \text{ mmol/L}$;
 - ✓ HbA1c 5.7-6.4% (39-47 mmol/mol)
3. Dyslipidemia meets one of the following conditions:
 - ✓ Fasting LDL-C $\geq 3.4 \text{ mmol/L}$ and $< 4.9 \text{ mmol/L}$, and $\text{TG} \leq 5.6 \text{ mmol/L}$
 - ✓ Fasting non-HDL-C $\geq 4.1 \text{ mmol/L}$ and $< 5.7 \text{ mmol/L}$, and $\text{TG} \leq 5.6 \text{ mmol/L}$
4. Completed one-week Patient diary, recorded at least 5 days in a week.

3.2 Exclusion Criteria

1. Patient with proven or documented atherosclerotic cardiovascular disease (ASCVD) including Acute coronary syndrome (ACS), history of myocardial infarction (MI), stable or unstable angina pectoris, coronary or other revascularization, ischemic stroke, transient ischemic attack and peripheral vascular disease (PAD),etc.

2. Diagnosed diabetes

According to 2021 the American Diabetes Association (ADA) “Standards of Medical Care in Diabetes”

✓ FPG \geq 126 mg/dL (7.0 mmol/L).

✓ 2-h PG \geq 200 mg/dL (11.1 mmol/L) during OGTT.

✓ A1C \geq 6.5% (48 mmol/mol).

✓ In a patient with classic symptoms of hyperglycemia or hyperglycemic crisis, a random plasma glucose \geq 200 mg/dL (11.1 mmol/L).

3. Patients with any lipid lowering drugs in the previous 3 months, including but not limited to statins, bile acid sequestrants, cholesterol absorption inhibitors, PCSK9 inhibitors, nicotinic acid, fibric acid derivatives, fibrates, other traditional Chinese medicine and n-3 fatty acids.

4. Patients with any antidiabetic drugs.

5. Contraindications to XZK or Atorvastatin:

✓ Allergic to XZK or Atorvastatin.

✓ Pregnancy or breastfeeding

6. Uncontrolled hypertension (systolic blood pressure \geq 180 mm Hg and/ or diastolic blood pressure \geq 110 mm Hg) at screening.

7. Active liver disease or hepatic dysfunction, including continuously elevated liver transaminase due to unknown causes. Abnormal liver function test at baseline (ALT or AST $>$ 3 \times ULN).

8. Known renal dysfunction or elevated serum creatinine levels at baseline (with an eGFR \leq 60 mL/min/1.73 m²).

9. Other endocrine diseases that might influence the levels of lipid or lipoprotein, such as hypothyroidism.

10. Patient has participated in clinical trials of other drugs in the past three months.

11. Previous statin treatment causes creatine kinase (CK) increased 10 times, or myalgia myopathy (muscle pain or muscle weakness, accompanied by Creatine phosphokinase (CK) exceeds 10 times the ULN)
12. Estimated life expectancy < 6 months at the time of enrollment
13. Abuse of alcohol, or history of alcohol abuse.
14. Close affiliation with the investigators, e.g., a close relative for the investigator, dependent person (e.g., employee or student of the investigators)

3.3 Subject enrolment and randomization

3.3.1 Number of Centers

This study will include approximately 20 sites in China.

3.3.2 Number of Participants

There will be approximately 392 subjects randomized in this study. Justification for the sample size can be found in 8.1 Sample Size estimate.

3.3.3 Randomization

Participants will be randomized using Interactive Web Response System(IWRS), which is an online, central randomisation service. Allocation concealment will be ensured, as the service will not release the randomization code until the patient has been recruited into the trial, which takes place after all baseline measurements have been completed.

All patients who give consent for participation and who fulfill the eligibility criteria will be randomized. Randomization will be requested by the investigator. In return, IWRS will send an answer form to the investigator who is not involved in assessing outcome of the study. The investigator will find the treatment condition to be conducted in this patient. The therapist then gives the information about treatment allocation to the patient. Staff responsible for outcome adjudication is not allowed to receive information about the group allocation.

The assessor regarding clinical outcomes will go through a profound assessment training program. The laboratory assessments will be marked by subject ID and performed by blinded. Randomization will occur within 3 days after the Laboratory result of randomization visit reported .

3.4 Procedures for handling incorrectly enrolled or randomized subjects

Subjects who fail to meet the inclusion/meet exclusion criteria should not, under any circumstances, be enrolled or received study medication. There can be no exceptions to this rule. Subjects who are enrolled, but subsequently found not to meet all the eligibility criteria must be withdrawn from the study. This has to be documented.

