3.7. Discontinuation of Study Drug

3.7.1. Permanent Discontinuation of Study Drug

For all participants who permanently discontinue study medication, the participants will still be part of the study, and outcome events and vital status must be reported until the common study end date. Discontinuing an investigational drug is usually the only available therapy to treat suspected Drug-Induced Liver Injury (DILI) , drug-induced kidney injury(DKI),and may not result in an immediate improvement as test values and symptoms can last (sometimes even progress) for days or weeks after the drug has been discontinued. Once discontinued, patients should not be re-exposed

to the suspected drug.

The study drugs should be discontinued in case

1) Meeting the criteria of possible Drug-Induced Liver Injury(FDA guidance)

- ALT or AST >8 ULN
- ALT or AST >5 ULN for more than 2 weeks
- ALT or AST >3 ULN and (TBL >2 ULN or INR >1.5)
- ALT or AST >3 ULN with the appearance of fatigue, nausea, vomiting, right upper quadrant pain or tenderness, fever, rash, and/or eosinophilia (>5%)

2) Diagnosis of rhabdomyolysis

● The clinical manifestations of rhabdomyolysis include myalgias, weakness, red to brown urine due to myoglobinuria, and elevated serum muscle enzymes. An acute elevation in the CK and other muscle enzymes and a decline in these values within three to five days of cessation of muscle injury. The CK is typically at least five times the upper limit of normal and is frequently greater than 5000 international units/L. The degree of myalgias and other symptoms varies widely, and some patients are asymptomatic. Fever, malaise, tachycardia, and gastrointestinal symptoms may be present.

● Other manifestations include fluid and electrolyte abnormalities, many of which precede or occur in the absence of acute kidney injury, and hepatic injury. Hypovolemia, hyperkalemia, hyperphosphatemia, hypocalcemia, hyperuricemia, and metabolic acidoses may be seen. Hyperkalemia may result in cardiac dysrhythmias. Later complications include acute kidney injury (AKI), hypercalcemia, compartment syndrome, and, rarely, disseminated intravascular coagulation.

3) Pregnancy;

4) The investigator considers that study drug is harmful to the safety or health of the participants;

5) Participants request to stop using the test drug;

6) Sponsor requires participants to permanently stop taking study drug

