3.8. Participant Discontinuation from the study treatment

An excessive rate of participant discontinuations from either treatment or “drop-outs” from the study may render the trial non-interpretable. In this study, HbA1C data are crucial to the primary analysis and must be collected until the end of the study, even if participants are no longer taking study medication. Therefore, all efforts will be taken to

motivate participants to comply with all study procedures and to continue to be followed until the end of the trial.

Participants should be specifically asked about any possible AE or other reasons that led to their decision to withdraw from the study, and all AE information obtained should be recorded. Participants may withdraw their informed consent orally or in writing, and they are advised to withdraw informed consent in writing

The investigator and participant must discuss and determine further follow-up options. Options for follow-up are listed below, in descending order of preference:

1. Participant continues the regular study clinic visits at the investigator's site as outlined in the protocol.
2. Participant will be contacted by phone at the regular follow-up intervals.
3. Participant allows his/her general practitioner or a family relative to be contacted at the regular follow-up interval.
4. Participant will be contacted once at the end of the study.
5. Participant withdraws consent. This will be the last option and means that the participant does not agree to any kind of follow-up and specifically refuses any further contact with the investigator. This should happen only in exceptional cases. If possible by local regulations, this decision will be provided in writing. Vital status will be obtained at study end through public information according to local guidelines and as allowed by local regulations. For participants who do not agree to attend regular study visits, the investigator will encourage the participant to return to the clinic for at least one final visit in order to perform all assessments as outlined for the end of Study(EOS) visit.

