3.9 Lost to Follow up

We define loss to follow-up as incomplete ascertainment of the primary outcome for participants randomized in the trial.

All attempts will be made to find all participants.

The following actions must be taken if a participant fails to return to the clinic for a required study visit:

- The site must attempt to contact the participant and reschedule the missed visit as soon as possible and counsel

the participant on the importance of maintaining the assigned visit schedule and ascertain whether or not the participant wishes to and/or should continue in the study.

- Before a participant is deemed lost to follow up, the investigator or designee must make every effort to regain contact with the participant (where possible, 3 telephone calls and, if necessary, a certified letter to the participant’s last known mailing address or local equivalent methods). These contact attempts should be documented in the participant’s medical record.

- If all attempts fail, depending on local legislation, death or other registries may be accessed or private investigation to locate a participant may be initiated.

- All randomly enrolled cases, no matter whether they fall off or not, should be recorded and retained, which can be kept as a file. It can also be used as the original record of Intention-To-Treat (ITT) analysis data.

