7.4 Storage

Only participants enrolled in the study may receive study drug and only authorized site staff may supply or administer study drug. All study drugs must be stored in a secure, environmentally controlled, and monitored (manual or automated) area in accordance with the labeled storage conditions with access limited to the investigator and authorized site staff. The investigator, institution, or the head of the medical institution (where applicable) is responsible for study drug accountability, reconciliation, and record maintenance (i.e., receipt, reconciliation, and final disposition records).

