8.3 Definitions of analysis sets

The full analysis set (FAS) includes all randomized subjects who received at least 1 dose of IP (investigational product) and have a non-missing HbA1c value at week 24. This analysis set will be used in both efficacy and safety analyses.

The Completer Analysis Set (CAS) includes subjects in FAS who completed IP and have a non-missing HbA1c value at week 24.

In all analysis sets, unless specified otherwise, subjects will be analyzed according to the ITT principle.

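### Section 3.4 withdraws ineligible subjects from the study without exempting those already randomised, which conflicts with the protocol's own follow-up rules and ITT principle

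*Protocol*

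**What the plan says.** Section 3.4 of the protocol is headed "Procedures for handling incorrectly enrolled or randomized subjects". Its rule for errors found later is: "Subjects who are enrolled, but subsequently found not to meet all the eligibility criteria must be withdrawn from the study". The only other requirement is that this be documented. The section does not distinguish stopping study drug from leaving the study, does not say whether visits continue, and does not refer to the follow-up options in 3.8.

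Other sections take the opposite line on follow-up:

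- 3.7.1: "For all participants who permanently discontinue study medication, the participants will still be part of the study".
- 3.7.3: every attempt is made to have participants attend all follow-up visits, whether or not they have stopped study drug.
- 3.8: HbA1c data "must be collected until the end of the study, even if participants are no longer taking study medication". Ending all contact is the last of five options, is tied to withdrawal of consent, and is meant to be exceptional.
- 3.9: a randomised participant whose primary outcome is not fully ascertained counts as lost to follow-up, and all attempts are to be made to find all participants.

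Section 8.3 states the ITT principle for the analysis sets. It defines the full analysis set (FAS) as "all randomized subjects who received at least 1 dose of IP (investigational product) and have a non-missing HbA1c value at week 24" and adds: "This analysis set will be used in both efficacy and safety analyses".

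**The concern.** A site that discovers, after allocation, that a subject did not meet a criterion has two incompatible instructions: remove the subject from the study, or keep collecting HbA1c to the end. The more specific one, 3.4, points to removal.

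Eligibility is fixed before allocation, but its discovery is not. Treatment is open-label, so people who know the arm can look for, or act on, an eligibility error differently in the two arms. Ending follow-up on that ground is an exclusion after randomisation. It is also irreversible: no statistical analysis plan can recover a week-24 HbA1c that was never measured. What is at stake is the randomised comparison and, to a lesser degree, safety follow-up. Precision is hardly affected.

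**Working it through.** **1. Does 3.4 reach randomised subjects?** The operative sentence says enrolled, but the heading names randomised subjects and the text gives them no other rule. Elsewhere the word extends past randomisation: 7.4 says "Only participants enrolled in the study may receive study drug", and 3.9 speaks of cases that were randomly enrolled. If the sentence were confined to the time before randomisation, the randomised subjects in the heading would have no rule at all.

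**2. Route to the analysis.** A subject who took at least one dose and whose visits stop before week 24 has no week-24 HbA1c. The FAS requires that value, so the subject is outside the FAS. A subject never dosed is outside it in any case, through the one-dose condition. Because the FAS also serves safety, the dosed subject would be missing from FAS-based safety tables too.

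**3. The plan's own sample size.** Inputs from 8.1: difference 0.3, SD 1.0, 80% power, 5% significance (reproduces as two-sided), 10% dropout.

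- Normal approximation: n = 2 × (1.96 + 0.8416)² / 0.3² = 174.4, so 175 per arm. The noncentral t gives 176, with power 80.1%.
- 176 / 0.90 = 195.6, so 196 per arm and 392 in total. The stated figures reproduce.

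**4. Scale of the problem.** The protocol gives no rate of misrandomisation. Assume 1% to 5%.

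- 392 × 0.01 = 3.9 and 392 × 0.05 = 19.6 subjects.
- Planned dropout is 392 × 0.10 = 39.2, so these are 10% and 50% of the allowance. Inside the allowance, planned power is unchanged.
- On top of the allowance, with power = Φ(0.3 × √(n/2) − 1.96):

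| Extra removal | n per arm | Power |
|---|---|---|
| none | 352.8 / 2 = 176.4 | 80.4% |
| 1% | (352.8 − 3.9) / 2 = 174.4 | 80.0% |
| 5% | (352.8 − 19.6) / 2 = 166.6 | 78.2% |

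**5. Possible bias (all inputs assumed).** Remove fractions p₁ and p₂ of the two arms, whose mean HbA1c change differs by d from the rest of their arm. With the same d in both arms, the difference shifts by (p₁ − p₂) × d.

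- 1% in one arm only, d = 0.5: 0.01 × 0.5 = 0.005, or 2% of 0.3.
- 5% against 1%, d = 0.5: 0.04 × 0.5 = 0.02, or 7% of 0.3.
- 5% in one arm only, d = 1.0 (a full planned SD): 0.05 × 1.0 = 0.05, or 17% of 0.3. This is an unlikely extreme.

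**The case against.** The best defence is that 3.4 is a specific rule for a different group. Section 3.7.1 lists six reasons for stopping study drug and ineligibility is not among them; 3.8 deals mainly with participants who choose to stop. Enrolled is also ambiguous: the visit plan puts an enrolment period before baseline, and the Appendix 1 log separates recruited from randomised. This shows that the text can be read more than one way. It does not reconcile it, because nothing exempts ineligible randomised subjects from the HbA1c rule in 3.8, and the heading of 3.4 still includes them.

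It is also fair that cases should be uncommon. Visit 1 and the randomisation system (9.5.1) both check eligibility before allocation, and laboratory testing is blinded (3.3.3). That limits frequency and selective discovery but does not exclude them.

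Four stronger readings may tempt a reader, and the protocol does not support them:

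- **That safety data are lost outright.** Adverse events are collected from consent through the study (6.4.1), serious events are followed to resolution or stability (6.4.2), unresolved events are followed as medically indicated (6.5), and 6.4.3 promises that all collected events will be summarised in the final report. What remains is narrower: absence from FAS-based safety tables, which comes from the week-24 condition in 8.3 and affects anyone without that value, and later scheduled safety assessments not made.
- **That 3.9 forbids removal through its retention sentence.** "All randomly enrolled cases, no matter whether they fall off or not, should be recorded and retained" concerns records, and can coexist with the duty to document in 3.4. The conflict with 3.9 lies in its definition of loss to follow-up.
- **That 3.5 confirms the end of follow-up.** Its statement that a withdrawn subject can no longer take part sits in a rule on reuse of subject IDs, for subjects who withdraw.
- **That visit 1 allows randomisation before eligibility is known**, because history and medications are listed after it. Item 1 of that visit already requires all criteria to be verified first.

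**Conclusion.** The point stands as an internal conflict that should be corrected. As written, 3.4 directs study withdrawal of randomised subjects found ineligible, against 3.7.1, 3.7.3, 3.8, the loss-to-follow-up definition in 3.9 and the ITT principle in 8.3.

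The harm is conditional. The protocol does not state that a withdrawn subject has no week-24 HbA1c; that follows only if sites take withdrawal to end follow-up, which is a natural reading since 3.4 provides none. Nor does any passage show that discovery would in fact differ by arm.

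The size is small. It rests on assumed rates of 1% to 5%, an assumed imbalance between arms and an assumed difference in HbA1c change. Power stays between 78.2% and 80.4%, and the illustrative bias is 2% to 7% of the planned effect outside the extreme case. The planned 392 need not change. The case for acting is that the lost values cannot be recovered and the correction is cheap.

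**What to change.** Reconcile 3.4 with 3.7.1, 3.7.3, 3.8 and 3.9:

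- Limit withdrawal from the study on grounds of ineligibility to subjects not yet randomised.
- For a randomised subject found ineligible, state that the case is documented as a protocol deviation, that the subject is asked to remain in HbA1c and safety follow-up to week 24, and that the subject is analysed in the assigned arm.

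How study drug is handled in these subjects is a clinical matter and is not addressed here.

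The cost is a few sentences in an amendment and, at the assumed rates, the remaining scheduled visits of about 4 to 20 subjects.
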